10.6 Early Withdrawal Visit

Record any Adverse Experiences and/or Review subject diary for adverse experiences and exclusionary medication use.

Record changes to concomitant medications.

Perform complete physical examination.

Perform and record vital signs.

Collect blood for clinical laboratory tests: Chemistry, Hematology, Urinalysis, Pregnancy (urine or serum).

11 ADVERSE EXPERIENCE REPORTING AND DOCUMENTATION

11.1 Adverse Events

An adverse event (AE) is any untoward medical occurrence in a clinical investigation of a patient administered a pharmaceutical product and that does not necessarily have a causal relationship with the treatment. An AE is therefore any unfavorable and unintended sign (including an abnormal laboratory finding), symptom or disease temporally associated with the administration of an investigational product, whether or not related to that investigational product. An unexpected AE is one of a type not identified in nature, severity, or frequency in the current Investigator's Brochure or of greater severity or frequency than expected based on the information in the Investigator's Brochure.

The Investigator will probe, via discussion with the subject, for the occurrence of AEs during each subject visit and record the information in the site's source documents. Adverse events will be recorded in the patient CRF. Adverse events will be described by duration (start and stop dates and times), severity, outcome, treatment and relation to study drug, or if unrelated, the cause.

AE Severity

The National Cancer Institute's Common Terminology Criteria for Adverse Events (CTCAE) Version 3.0 should be used to assess and grade AE severity, including laboratory abnormalities judged to be clinically significant. The modified criteria can be found in the study manual. If the experience is not covered in the modified criteria, the guidelines shown in Table 1 below should be used to grade severity. It should be pointed out that the term "severe" is a measure of intensity and that a severe AE is not necessarily serious.

Table 1. AE Severity Grading

Severity (Toxicity Grade)	Description
Mild (1)	Transient or mild discomfort; no limitation in activity; no medical intervention or therapy required. The subject may be aware of the sign or symptom but tolerates it reasonably well.
Moderate (2)	Mild to moderate limitation in activity, no or minimal medical intervention/therapy required.
Severe (3)	Marked limitation in activity, medical intervention/therapy required, hospitalizations possible.
Life-threatening (4)	The subject is at risk of death due to the adverse experience as it occurred. This does not refer to an experience that hypothetically might have caused death if it were more severe.

AE Relationship to Study Drug

The relationship of an AE to the study drug should be assessed using the following the guidelines in Table 2.

Table 2. AE Relationship to Study Drug

Relationship to Drug	Comment
Definitely	Previously known toxicity of agent; or an event that follows a reasonable temporal sequence from administration of the drug; that follows a known or expected response pattern to the suspected drug; that is confirmed by stopping or reducing the dosage of the drug; and that is not explained by any other reasonable hypothesis.
Probably	An event that follows a reasonable temporal sequence from administration of the drug; that follows a known or expected response pattern to the suspected drug; that is confirmed by stopping or reducing the dosage of the drug; and that is unlikely to be explained by the known characteristics of the subject's clinical state or by other interventions.
Possibly	An event that follows a reasonable temporal sequence from administration of the drug; that follows a known or expected response pattern to that suspected drug; but that could readily have been produced by a number of other factors.
Unrelated	An event that can be determined with certainty to have no relationship to the study drug.

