Naltrexone is well-tolerated and has no known significant drug interactions.⁵⁴ In randomized controlled trials, naltrexone has few serious side effects; it has no known abuse potential and dependence has not been reported.^{54, 66, 67, 69-72} Naltrexone's activity is believed to be due to both the parent compound and the 6-naltrexol metabolite.⁶⁹ The mean elimination half-life of for naltrexone and 6-naltrexol are four and 13 hours, respectively.⁶⁹ Initial trials evaluating the efficacy of naltrexone as treatment for alcohol dependence raised no safety concerns.^{65, 66} Naltrexone was also well-tolerated in subsequent studies in more clinically heterogeneous populations with co-morbid conditions.^{67, 112} Naltrexone has not been shown to cause significant increases in complaints in placebo-controlled trials in patients known to be free of opioids for more than 7 to 10 days.⁶⁹ The largest safety study to date on clinical use of naltrexone as a pharmacotherapy for treatment of alcoholism was a multi-center safety trial involving 865 individuals (500 naltrexone-treated patients, 238 patients in an unmedicated control group).⁶⁸ Results of this study demonstrated that the most commonly reported side effects were nausea (9.8%), headache (6.6%), dizziness (4.4%), nervousness (3.8%), and fatigue (3.6%); serious side effects were uncommon.⁶⁸ Naltrexone was discontinued in 15% of the participants, with nausea being the most common reason for medication discontinuation.⁶⁸ Studies in alcoholic populations and healthy volunteers have suggested that a small number of patients may experience an opioid withdrawal-like symptom complex including tearfulness, mild nausea, abdominal cramps, restlessness, arthralgia, myalgia, and nasal symptoms.⁶⁹ Naltrexone has no known sexual side-effects⁶⁹, supporting its potential acceptability for sexually-active MSM. Depression, suicidal ideation, and suicide attempts have been reported in both groups when comparing naltrexone and placebo for treatment for alcoholism.⁶⁹ There is no indication that naltrexone treatment increases the risk of suicide.⁶³

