9.2.5 Adverse Events

Potential AEs will be monitored using a checklist of most common AEs associated with naltrexone similar to prior Phase IV naltrexone studies¹¹ and will follow the "Division of AIDS Table for Grading the Severity of Adult and Pediatric Adverse Events" and UCSF IRB reporting guidelines.¹¹⁶ Safety monitoring will include the assessment, follow-up, and reporting of clinical/serious AEs (start and stop dates and times), severity/grade, outcome, treatment and relation to study drug will be recorded on the case report forms as well as in the electronic database.

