15.4 Analysis of Secondary Endpoints

The analysis of the secondary endpoint to determine the efficacy of targeted naltrexone versus placebo in reducing alcohol-associated sexual risk behaviors, we will use GEE Poisson models with robust standard errors for the four monthly ACASI assessments on numbers of male anal sex partners, HIV-serodiscordant unprotected anal sex partners, unprotected anal sex partners while intoxicated with alcohol, and unprotected anal sex events with serodiscordant partners, including the baseline value. In the event that these outcomes are severely over-dispersed, we will analyze indicators for any self-report of each behavior, using GEE logistic models. **MDEs:** Based on estimates of within-subject correlation and control prevalence from our Project Echo trial, we estimate that the study will have 80% power to detect 31% reductions in numbers of male anal sex partners, 57% reductions in SDUA partners, 46% reductions in UA partners while intoxicated with alcohol, and 56% reductions in UA events with serodiscordant partners. In analyses using GEE logistic models, we will have 80% power to detect reductions of 14%, 38%, 39%, and 30% in any report of these four sexual risk behaviors, respectively.

Safety and tolerability data will be summarized by treatment group.

Adverse event rates will be coded by body system and MedDra classification term. Adverse events will be tabulated by treatment group and will include the number of patients for whom the event occurred, the rate of occurrence, and the severity and relationship to study drug.

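### The causality table in section 11.1 is not exhaustive and, read literally, not mutually exclusive, so the relationship-to-drug column planned in section 15.4 can mislead

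*Combined protocol and SAP*

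**What the plan says.** Table 2 of section 11.1 (AE Relationship to Study Drug, not the procedures table in the appendix) has four rows.

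- *Definitely* has two limbs joined by a single connective: "Previously known toxicity of agent; or an event that follows a reasonable temporal sequence from administration of the drug". The second limb goes on to require a known pattern and confirmation on stopping or reducing the drug, and closes with "and that is not explained by any other reasonable hypothesis".
- *Probably* needs reasonable timing and an event "that follows a known or expected response pattern to the suspected drug; that is confirmed by stopping or reducing the dosage of the drug", with other explanations unlikely.
- *Possibly* needs reasonable timing and an event "that follows a known or expected response pattern to that suspected drug; but that could readily have been produced by a number of other factors".
- The last row, *Unrelated*, is "An event that can be determined with certainty to have no relationship to the study drug".

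Section 11.1 also defines an unexpected AE, has the investigator probe for events at each visit, and asks for the cause of any event called unrelated. Section 9.2.5 adds solicitation by a "checklist of most common AEs associated with naltrexone". Section 15.4 tabulates events by arm with patient counts, rates, and "the severity and relationship to study drug".

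**The concern.** A causality scale has to give each event one code. This one fails in two ways.

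First, it has a gap. The protocol expects unexpected events, since it defines them. Yet every related row asks for a known or expected pattern or a known toxicity, and the only unrelated row asks for certainty. An unexpected event that starts soon after a capsule and has no proven other cause matches nothing. Nor does a poorly timed event of unfamiliar type that cannot be excluded with certainty.

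Second, it overlaps. If the opening words of *Definitely* stand alone, a known toxicity qualifies whatever its timing and whatever else might explain it. Items on the section 9.2.5 checklist are known naltrexone effects, so they meet that limb in both arms. A headache the morning after heavy drinking could then be *Definitely* and *Possibly* at once.

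At stake is whether the relationship column in the safety table means the same thing from one event, or one rater, to the next.

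**Working it through.** The documents give no figure to reproduce. The check is one of logic, followed by an illustration of scale.

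**Step 1. The criteria side by side (Table 2, section 11.1)**

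| Row | Timing | Known pattern | Confirmed on stopping or reducing | Other explanation |
|---|---|---|---|---|
| *Definitely*, first limb, literal | not asked | known toxicity | not asked | not asked |
| *Definitely*, second limb | required | required | required | none reasonable |
| *Probably* | required | required | required | unlikely |
| *Possibly* | required | required | not asked | readily available |
| *Unrelated* | not asked | not asked | not asked | certain: no relation |

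**Step 2. Enumerate the cases**

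Timing, pattern and confirmation are each yes or no. Other explanation is none, unlikely, ready, or certainly unrelated. That gives 2 × 2 × 2 × 4 = 32 combinations. Known toxicity is treated as the same feature as known pattern, and having no other explanation is taken to satisfy *Probably* as well. Two readings of *Definitely* are tried: literal (a known toxicity suffices) and alternative (all later conditions apply to both limbs).

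| Reading | No row | One row | Two rows |
|---|---|---|---|
| Literal | 12 | 12 | 8 |
| Alternative | 20 | 11 | 1 |

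**Step 3. Which cases fail**

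- Literal, no row: pattern not known and not certainly unrelated, 2 (timing) × 2 (confirmation) × 3 (explanation) = 12. Six are well timed and six poorly timed.
- Literal, two rows: *Definitely* with *Probably* 2, with *Possibly* 2, with *Unrelated* 4; 2 + 2 + 4 = 8.
- Alternative, no row: the same 12, plus 6 poorly timed known-pattern cases, plus 2 that are well timed with a known pattern, no confirmation on stopping, and no or only an unlikely other explanation; 12 + 6 + 2 = 20.
- Alternative, two rows: 1, where *Definitely* sits inside *Probably*.

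All 6 well-timed, unexpected, not-certainly-unrelated cases lack a row under both readings. These are counts of logical cases, not proportions of the events the trial will see.

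**Step 4. How common the known symptoms might be**

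Inputs: 60 per arm (section 8.1) and the side-effect rates that section 2.1 cites from a safety study in the treatment of alcoholism.

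| Symptom | Rate | × 60 |
|---|---|---|
| Nausea | 9.8% | 5.9 |
| Headache | 6.6% | 4.0 |
| Dizziness | 4.4% | 2.6 |
| Nervousness | 3.8% | 2.3 |
| Fatigue | 3.6% | 2.2 |
| Sum | 28.2% | 16.9 |

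Between 5.9 men (complete overlap of symptoms) and 16.9 men (no overlap) of 60 on naltrexone would report at least one of the five.

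No placebo rate is given. Assuming placebo nausea of 2%, 5% or 9.8%, the expected number of 60 is 1.2, 3.0 or 5.9. The chance of at least one, 1 − (1 − p)^60, is 0.702, 0.954 or 0.998. On the literal reading each such man could be coded *Definitely* related to a drug he did not receive.

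**The case against.** The case for leaving the table alone has real force.

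- *The sentence is ambiguous.* On the alternative reading the closing conditions also govern known toxicities. Even literally, the table permits *Definitely* without dictating it, because another row may fit too. This stands against a reader inferring that every solicited event is automatically *Definitely* and the column carries no information. Nor is the column confined to checklist items: section 11.1 has the investigator probe more widely and counts abnormal laboratory findings. The alternative reading does not rescue the table, however, since it leaves more cases without a row.
- *Unexpected events are not lost.* Section 11.2.1 documents all SAEs whether or not related. Section 17.2 sends SAEs to the IRB regardless of causality and also covers unexpected experiences. Section 14 gives the DSMB adverse events in total and by group. None of this uses the rating, and it stands in full.
- *The randomised comparison is intact.* Counts, rates and severity by arm are independent of the code, and raters are blinded (section 8.2). This also stands.
- *Timing is available.* It is tempting to say that dose timing is missing from the safety data. It is not. Onset times are recorded (9.2.5, 11.1), MEMS openings are logged in real time (8.6, 9.2.3), daily texts collect dosing (9.2.4), and weekly visits record events and download MEMS data together (10.4). The plan only omits to say that the rater should use them.
- *Table 2 is offered as guidelines.* Raters may improvise, but improvised coding is the inconsistency that a written table should prevent.

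**Conclusion.** The point holds in a limited form. The gap for unexpected events exists on either reading and needs no assumption beyond the wording of the table. The overlap depends on the literal reading, which is the natural one grammatically but not the only one.

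A reader might conclude that the relationship column is wrong in both directions. The documents do not support that. Over-attribution follows only if raters apply the first limb literally and choose *Definitely* over another row that also fits. Under-attribution is not forced either: an unexpected event is left without a code, not placed in *Unrelated*, which demands certainty. What can be said is that the column cannot be filled consistently and so can mislead.

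The effect is confined to that descriptive column. The 5.9 to 16.9 of 60 only illustrates how many naltrexone participants might report the five named symptoms, at rates carried over by assumption from a different population. It does not count misclassified events. The repair is cheap and worth making.

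**What to change.** Amend Table 2 of section 11.1.

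1. In *Definitely*, delete the free-standing known-toxicity alternative. Keep all remaining conditions, including confirmation on stopping or reducing the drug.
2. Redefine *Possibly* as reasonable timing, whether or not the pattern is known, where a relationship to drug cannot be excluded and the criteria for *Probably* or *Definitely* are not met.
3. Add *Unlikely*: an event without reasonable timing that cannot be excluded with certainty. Leave *Unrelated* as it is.
4. State that the rater uses the time from the last MEMS opening or text-reported dose to event onset, derived from data already collected.

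Run against the same 32 combinations, this gives *Definitely* 1, *Probably* 1, *Possibly* 10, *Unlikely* 12 and *Unrelated* 8; 1 + 1 + 10 + 12 + 8 = 32, so none is left without a row. The single *Definitely* case still also meets *Probably*; a note that *Probably* applies only when *Definitely* is not met removes that overlap.

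The cost is protocol and case report form wording, plus blinded recoding of any events already rated. No new procedure or data collection is needed.

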11.2 Serious Adverse Experiences (SAE)

An SAE is defined as any AE occurring at any dose that results in any of the following outcomes:

- death
- a life-threatening adverse experience
- inpatient hospitalization or prolongation of existing hospitalization
- a persistent or significant disability/incapacity
- a congenital anomaly/birth defect

Other important medical events may also be considered an SAE when, based on appropriate medical judgment, they jeopardize the subject or require intervention to prevent one of the outcomes listed.

11.2.1 Serious Adverse Experience Reporting

Study sites will document all SAEs that occur (whether or not related to study drug) per [UCSF CHR Guidelines](#). The collection period for all SAEs will begin after informed consent is obtained and end after procedures for the final study visit have been completed.

12 DISCONTINUATION AND REPLACEMENT OF SUBJECTS

12.1 Early Discontinuation of Study Drug

A subject may be discontinued from study treatment at any time if the subject or the investigator feels that it is not in the subject's best interest to continue. The following is a list of possible reasons for study treatment discontinuation:

Subject withdrawal of consent (or assent)

Subject is not compliant with study procedures

Adverse event that in the opinion of the investigator would be in the best interest of the subject to discontinue study treatment

Protocol violation requiring discontinuation of study treatment

Lost to follow-up

PI or clinician request for early termination of study

Positive pregnancy test (females)

If a subject is withdrawn from treatment due to an adverse event, the subject will be followed and treated by the Investigator until the abnormal parameter or symptom has resolved or stabilized.

All subjects who discontinue study treatment should come in for an early discontinuation visit as soon as possible and then should be encouraged to complete all remaining scheduled visits and procedures.

All subjects are free to withdraw from participation at any time, for any reason, specified or unspecified, and without prejudice.

Reasonable attempts will be made by the investigator to provide a reason for subject withdrawals. The reason for the subject's withdrawal from the study will be specified in the subject's source documents. Refer to Section 10 for early termination procedures.

12.2 Withdrawal of Subjects from the Study

A subject may be withdrawn from the study at any time if the subject or the investigator feels that it is not in the subject's best interest to continue.

All subjects are free to withdraw from participation at any time, for any reason, specified or unspecified, and without prejudice.

Reasonable attempts will be made by the investigator to provide a reason for subject withdrawals. The reason for the subject's withdrawal from the study will be specified in the subject's source documents. As noted above, subjects who discontinue study treatment early (i.e., they withdraw prior to Week 8 Visit) should have an early discontinuation visit. Refer to Section 10 for early

termination procedures. Subjects who withdraw after Week 8 Visit but prior to Week 12 Visit should be encouraged to come in for a final visit (and the procedures to be followed would include those for their next scheduled visit).

12.3 Replacement of Subjects

Subjects who withdraw from the study treatment will not be replaced.

13 PROTOCOL VIOLATIONS

A protocol violation occurs when the subject or investigator fails to adhere to significant protocol requirements affecting the inclusion, exclusion, subject safety and primary endpoint criteria. Protocol violations for this study include, but are not limited to, the following:

Failure to meet inclusion/exclusion criteria

[figure not shown]
Use of a prohibited concomitant medication (such as opiate medications)

Failure to comply with Good Clinical Practice (GCP) guidelines will also result in a protocol violation. The PI will determine if a protocol violation will result in withdrawal of a subject.

When a protocol violation occurs, it will be discussed with the investigator and a Protocol Violation Form detailing the violation will be generated. This form will be signed by a Sponsor representative and the Investigator. A copy of the form will be filed in the site's regulatory binder and in the Sponsor's files.

14 DATA SAFETY MONITORING

The PI along with the site physician [name], will be responsible for ensuring proper monitoring of the safety and efficacy of this trial, including the execution of the DSM plan, and complying with the reporting requirements, including reports to the IRB, DSMB, NIDA and (where applicable) the FDA (see Figure 1 below).

The research team including the PI, clinicians, data manager, research associates, and recruitment coordinator, meets weekly to discuss all aspects of the study such as recruitment and retention, clinical or counseling issues, and any regulatory or operation issues. All study documents are monitored by the study coordinator for quality assurance on a weekly basis to ensure timely

corrections to charting such as missing initials or cross-outs with error-correction. Although there is no outside monitor, the clinicians review each other's charts for accuracy, consistency, and adherence to protocol. Regular audits will be conducted as well on consent forms, laboratory logs and other data collection forms.

The interim DSMB report will contain a brief description of the trial, baseline socio-demographic characteristics of participants, retention and disposition of study participants, a description of any quality assurance or regulatory issues, a report of AEs and SAES, and the status of outcome data.

Members and affiliation: We will use the existing University of California, Los Angeles (UCLA) Data & Safety Monitoring Board for Addiction Medicine (DSMBAM), which has extensive experience in monitoring pharmacologic interventions, including among vulnerable populations. The DSMBAM has monitored all of our pharmacologic trials for substance users.

To ensure that the DSMB oversight of the study remains independent from the proposed study, the PI([name]) as well as others who serve on the DSMBAM that might be linked with the study in some way recuse themselves from review of the present study.

The purpose of the DSMBAM is to provide oversight and monitoring of Phase I and Phase II clinical trials of pharmacological and behavioral treatments for stimulant dependence. There are three fundamental charges of the board, which are:

- To ensure the safety of trial participants
- To preserve validity and integrity of research data
- To facilitate the availability of timely as well as reliable findings to the broader clinical community

Below are members who serve as committee chairs as well as clinical research experts:

